1.1. Study design

This study is a monocentric, prospective, randomized, open-blinded endpoint (PROBE) (17) phase II clinical trial designed to evaluate the effectiveness of a cognitive training intervention compared to a control intervention [Progressive Muscle Relaxation; PMR (18)] in patients with post-COVID subjective or objective cognitive impairment (primary endpoint).

Patients with post-COVID cognitive impairment participate in a three-week intervention program consisting of nine sessions (three per week) of either cognitive training or PMR (18) (open-label interventions). In the cognitive training group, participants are further divided into two subgroups: half receive anodal tDCS while the other half receive sham tDCS in a double-blinded, sham-controlled manner (secondary endpoint). Thus, participants are randomly allocated to one of three study arms: (1) cognitive training with anodal tDCS over the left dorsolateral prefrontal cortex (DLPFC); (2) cognitive training with sham tDCS over the left DLPFC; or (3) PMR with sham tDCS.

Random allocation to these three groups is done through a stratified block randomization method with variable block length, using a 1:1:1 ratio. The stratification is based on participants' performance in the n-back task during pre-assessment, with two strata: those scoring $\leq 87\%$ correct and those scoring > 87% correct. The randomization sequences are generated software's blockrand package using the R (https://CRAN.Rproject.org/package=block- rand; http://www.R-project.org). Following a telephone screening and baseline assessment, eligible participants who provide written informed consent are randomly assigned to a study arm according to the generated randomization sequence within each block and performance stratum.

Secondary hypotheses related to the comparison of the two cognitive training arms with active or sham tDCS, will be evaluated in a double-blinded, sham-controlled manner.

[figure not shown]

Figure 1. Neuromod-COV study flowchart. tDCS: transcranial direct current stimulation; PMR: Progressive Muscle Relaxation. Obtained from Neuromod-COV study protocol (14).

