4.3. Safety outcomes

Safety is assessed through an adapted (22) self-report questionnaire administered every third training day (V4, V7 and V10). This questionnaire asks participants to rate the intensity of various sensations, including itching, pain, burning, warmth/heat, metallic or iron taste, fatigue, decreased alertness, and others.

Table 1. Neuromod-COV outcome measures	. Adapted from Neuromod-COV	/ study protocol (14).
--	-----------------------------	------------------------

			Baseline	Pre (3 days before T1)	T1-T9 (9 sessions for 3 weeks)	Post (3 days after T9)	FU (1 month after Post)
			$\sim 3h$	~ 3h	~ 1h	~ 3h	~ 3h
Time point	Measurement	Mode	V0	V1	V2-V10	V11	V12
Enrollment							
Informed consent		Paper	Х				
Eligibility	Medical history	Paper	Х				
screening	Mini-DIPS (30)	Paper	Х				
Questionnaires	Demographics	Paper	Х				
Neuropsychological screening	VLMT (23) ROCF (31) DS (32) TMT(23) Stroop (33) PF (23) SF (23)	Paper	Х				
Intervention					← →		
Training tasks	Letter updating task (24)	Tablet-PC	Х	X	x ^a	Х	x
	PMR (18)	Instructed			x ^b		
Brain stimulation	tDCS (anodal vs. sham)	Device			х		

	Initial state questionnaire	Paper	X	Х	х	Х	Х
Quastiannairas	PANAS (34)	Paper			Х		
Questionnaires	Adverse events questionnaire ^c (22)	Paper			Х		
Additional assessm	nents						
Linturin ed te elve	n-back task (23)	Computer		Х		X ^d	Х
Virtual	Virtual reality task (25)	Computer		Х		Х	Х
	PROMIS® (29-Profile v2.1 & Cognitve functioning SF 8a v2.0; 28)	Paper		х		x	х
Questionnaires	Sleeping behavior: PSQI (35) ESS (36) MEQ (37)	Paper		x		x	х
	PCFS (29)	Paper		Х		Х	Х
General activity	Actigraphy	Device		х		Х	

T1-T9: trainings 1-9; FU: follow-up assessment; V0-V12: visits 0-12; Mini-DIPS: Brief Diagnostic Interview for Psychiatric Disorders; VLMT: German version of the auditory verbal learning test; ROCF: Rey-Osterrieth Complex Figure Test; DS: Digit Span Test; TMT: Trail Making Test. Stroop: Stroop Test; PF: Phonological fluency; SF: Semantic fluency; PMR: Progressive Muscle Relaxation; tDCS: transcranial Direct Current Stimulation.

PANAS: Positive and Negative Affect Schedule; PROMIS®: Patient-reported Outcome Measurement Information System; PSQI: Pittsburgh Sleep Quality Index; ESS: Epworth Sleepiness Scale; MEQ: Morningness-Eveningness Questionnaire; PCFS: Post-COVID Functional Scale.

^a Only for cognitive training groups.

^b Only for the PMR group.

^c Assessed every third training day (V4, V7 and V10).

^d Primary outcome

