6.3. Safety analysis

Safety outcomes will be reported as incidence (n & rates with 95% CI) both overall and by intervention groups, based on the safety analysis set. Incidence rates and corresponding 95% CIs will be estimated using Poisson regression models, which account for different observation periods across participants. Group comparisons will be conducted using incidence rate ratios and their 95% CIs. The safety analysis results will be interpreted and discussed comprehensively, including minor differences between groups.

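### Section 6.3 reduces graded intensity ratings to incidence, sets no event threshold or counting unit, and plans no comparison of intensity between active and sham tDCS

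*SAP*

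**What the plan says.** Section 4.3 describes the safety instrument as a graded one: "This questionnaire asks participants to rate the intensity of various sensations, including itching, pain, burning, warmth/heat", followed by taste, fatigue, decreased alertness and others. It is filled in three times per participant, at V4, V7 and V10.

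Section 6.3 sets out the analysis: "Safety outcomes will be reported as incidence (n & rates with 95% CI) both overall and by intervention groups". The model is "Incidence rates and corresponding 95% CIs will be estimated using Poisson regression models", and "Group comparisons will be conducted using incidence rate ratios and their 95% CIs". The section closes with a commitment on interpretation: "The safety analysis results will be interpreted and discussed comprehensively, including minor differences between groups".

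Two other places bear on this. The opening paragraph of section 6 promises, for every outcome and time point, descriptive statistics suited to the scale of the variable and given by group. Section 1.1 shows that every participant wears the device: two arms receive cognitive training with active or sham stimulation, and the third is "or (3) PMR with sham tDCS".

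**The concern.** The instrument measures how strong a sensation is, but the analysis describes how often something occurred. Section 6.3 does not connect the two. It does not say which grade turns a rating into an event, whether itching and pain are counted separately or together, or how the arms will be compared on intensity. It also refers to intervention groups without naming the contrast that would isolate stimulation.

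What is at stake is the tolerability statement for tDCS. If sensations occur about equally often under active and sham stimulation but are stronger under active, the planned ratios could support a statement of similar incidence and leave the difference in tolerability out of the formal comparison. This information is already collected and costs little to use.

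**Working it through.** **Plan's own figures.** The SAP gives no sensation rates, number of grades or precision target for safety. The only figure used from it is the arm size: 60 participants (section 1.4) allocated 1:1:1 (section 1.1) gives 60 / 3 = 20 per arm. The total of 60 itself reproduces (40 vs 20, d = 0.8, two-sided 5%, noncentral t: power 0.819), but it concerns the primary outcome and has no bearing here.

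**Step 1: measurement against analysis.**

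| Element | Section 4.3 | Section 6.3 |
|---|---|---|
| Scale | graded intensity per sensation | incidence (n and rates) |
| Repeats | V4, V7, V10 | Poisson rate over observation period |
| Event threshold | not stated | not stated |
| Per sensation or pooled | sensations listed separately | not stated |
| Between-arm comparison | – | incidence rate ratio only |

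**Step 2: what the ratio can show.** Assumed inputs: a sensation is reported on a fraction p of questionnaires in both arms. Among reports, grades 1/2/3 split 80/15/5% under sham and 30/40/30% under active. The ratio (active / sham) then depends on the threshold alone:

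- any intensity: (p × 1.00) / (p × 1.00) = 1
- grade 2 or higher: p × (0.40 + 0.30) / [p × (0.15 + 0.05)] = 0.70 / 0.20 = 3.5
- grade 3: (p × 0.30) / (p × 0.05) = 6

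So the same data give 1, 3.5 or 6 according to a rule that the SAP does not state. Whatever threshold is chosen, a shift in grade that does not cross it leaves the ratio unchanged.

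**Step 3: size of the loss under those splits.** Simulation with 20 vs 20 participants, three questionnaires, one sensation, within-person correlation, and 2000 runs per row. Events were counted at any intensity, as one possible reading. The rate ratio was tested by z = ln(c_active / c_sham) / √(1/c_active + 1/c_sham), where c is the number of reports in the arm. Intensity was compared by a rank test on each participant's mean rating.

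| Presence, sham vs active | Rate ratio test rejects | Intensity test rejects |
|---|---|---|
| 30% vs 30% | 6.7% | 10.5% |
| 50% vs 50% | 2.8% | 28% |
| 70% vs 70% | 0.6% | 67% |
| 90% vs 90% | 0.0% | 98% |
| 30% vs 50% | 41% | 73% |
| 50% vs 70% | 24% | 92% |
| 50% vs 80% | 54% | 99% |

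In the first four rows the true ratio is 1, so the rate ratio test has nothing to find. In the last three, frequency also differs and the ratio picks up part of the difference. The severity splits are deliberately far apart, so the table shows direction, not expected power.

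**Step 4: what the remedy can resolve.** Suppose moderate-or-stronger ratings occur in 20% vs 5% of participants (assumed). With 20 per arm that is 4 vs 1. The risk ratio is 4.0; SE of ln RR = √(1/4 − 1/20 + 1/1 − 1/20) = √1.15 = 1.07; 95% CI = exp(1.386 ± 1.96 × 1.07), about 0.5 to 33. Fisher's exact p = 0.34. A dichotomised severity count is inconclusive at this size, which is why the comparison should use all grades.

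**The case against.** The strongest reply is that intensity will be described anyway. Safety outcomes are listed among the analysis variables, and the opening of section 6 promises scale-appropriate descriptives for all outcomes by group. Read literally, that covers the ratings at V4, V7 and V10. This stands in part: intensity summaries may well appear in the report. But section 6.3, the specific rule for safety, does not take them up, and the general rule supplies neither an event threshold nor a comparison between arms. The choice of link function by scale at the end of section 6.2, which includes an ordinal option, does not close the gap either, because section 6.3 names Poisson regression.

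Two stronger readings are tempting. A reader might infer that any non-zero rating counts as an event, so that a faint itch weighs as much as severe pain. The SAP states neither that threshold nor pooling across sensations; it leaves both open. A reader might also infer that any active-versus-sham difference in severity would be missed. That goes too far: a difference that also changes frequency would partly show (24% to 54% rejection in the illustration), a higher threshold would catch shifts that cross it, and section 6.3 commits to discussing minor group differences. Nor does the SAP give rates to show that the arms would differ mainly in intensity.

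It is also fair to say that the remedy will not produce firm conclusions with 20 per arm, as step 4 shows, and that section 6.3 already allows an active-versus-sham comparison by reporting by group.

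**Conclusion.** The point holds in a limited form. Section 6.3 turns a graded measure into incidence without an event threshold or counting unit, and its only between-arm comparison is a rate ratio. A severity difference between active and sham stimulation that leaves event frequency unchanged cannot appear in that comparison.

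The size depends on unknown rates and severity splits. Under the assumed splits with equal frequency, the ratio is 1, 3.5 or 6 depending on the unstated threshold. Counting any intensity, the ratio test rejects in 0% to 6.7% of runs, against 10.5% to 98% for an intensity comparison. These are illustrations on assumed inputs, not predictions for this trial.

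This is an inexpensive improvement to the safety reporting. It does not touch the primary analysis, and it does not show that a harm would go unreported.

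**What to change.** Amend section 6.3 to state:

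1. Events are counted per sensation, with the intensity threshold given explicitly.
2. For each sensation and arm, the distribution of each participant's maximum intensity over V4, V7 and V10 is reported, with incidence at any intensity and at moderate-or-stronger intensity. The SAP does not list the questionnaire's grades, so the grade that counts as moderate must be written down.
3. Training + active vs training + sham is the tDCS tolerability contrast, because those arms share the same task.
4. Intensity is compared on that contrast by a method that uses all grades, such as a rank test on the maximum rating or an ordinal model, with the result labelled descriptive.

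The cost is a few sentences of SAP text and one further table from ratings already collected. The downsides are more descriptive rows and wide intervals for the stronger grades at about 20 per arm, so the output describes tolerability and does not confirm a difference or its absence.

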2.1. Definitions

The **full analysis set** will consist of all randomized participants who received at least one day of intervention. If participants withdraw informed consent after baseline assessment, they will be considered screening failures and, therefore, will not be included in the full analysis set. The

per-protocol analysis set comprises all subjects who received the full three weeks of intervention or control intervention and completed all visits in the treatment groups they were allocated to. Safety outcomes [see Safety outcomes section (22)] are assessed during tDCS intervention, and all participants who received at least one intervention will be included in the safety analysis set according to their actual treatment. Since no participant received other treatment as intended or switched treatment groups during the study, and no information on safety measures is available for participants who missed intervention or follow-up visits or dropped out, the safety analysis set is the same as the per protocol analysis set in this study.

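### Section 6.3 fits Poisson regression to sensations reported repeatedly by the same participants, without naming a counting unit or any handling of within-participant dependence, so its 95% CIs are not valid in general

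*SAP*

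**What the plan says.** Section 4.3 describes the safety data. A self-report form is given on every third training day, at V4, V7 and V10, and "This questionnaire asks participants to rate the intensity of various sensations". Seven sensations are named, followed by an open category. Section 6.3 sets the summary: "Safety outcomes will be reported as incidence (n & rates with 95% CI) both overall and by intervention groups". On the model it says "Incidence rates and corresponding 95% CIs will be estimated using Poisson regression models", and it describes these models as ones "which account for different observation periods across participants". For contrasts, "Group comparisons will be conducted using incidence rate ratios and their 95% CIs". The section closes by promising to discuss even small group differences.

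Section 6.3 names no random effect, clustered or robust variance, or dispersion term. It gives no rule that turns an intensity rating into an event. It does not say whether a participant counts once, once per visit, or once per sensation per visit. The repeated-measures efficacy models in sections 6.1 and 6.2, by contrast, each specify a subject random intercept.

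Section 2.1 adds that "the safety analysis set is the same as the per protocol analysis set in this study", and the per-protocol set consists of people who completed every visit.

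**The concern.** Poisson regression in its default form takes the variance of a count to equal its mean. Reports from one person at three visits, or on several sensations, are not independent draws: someone who feels itching at V4 may well feel it again at V7. An observation-time offset corrects for unequal exposure and does nothing for this dependence. In the other direction, a yes/no report has less variance than a Poisson count with the same mean. The two departures pull against each other, and which one wins depends on the counting unit, which the plan leaves open.

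At stake is how the safety rate ratios are read, including active versus sham tDCS with about 20 per arm. Intervals that are too narrow make chance differences look established. Intervals that are too wide hide differences in common sensations. A plan that intends to discuss small differences needs intervals with known coverage.

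The stated reason for choosing Poisson regression is also weak on the SAP's own terms. If the safety set is the completers, everyone attended all three questionnaire visits and observation periods hardly differ. The repeated reports remain.

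**Working it through.** **Plan's own figure.** The SAP gives no number for the safety analysis, so there is none to reproduce.

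**Inputs from the SAP.** Three questionnaire visits and seven named sensations (4.3); 60 participants, 40 training and 20 PMR (1.4); 1:1:1 allocation (1.1), hence 60/3 = 20 per arm; Poisson regression with rate ratios (6.3).

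**Assumptions, because the SAP gives neither.** p, the probability that a report is positive, and rho, the correlation between reports from the same person. Both are varied over a range. For pooled sensations one common p and rho are used, which is a simplification.

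**Formula.** With m yes/no reports per participant, the participant's count has mean mp and variance mp(1-p)(1+(m-1)rho). The Poisson model assumes variance mp. The ratio of true to Poisson variance is therefore

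(1-p)(1+(m-1)rho).

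If both arms share p and rho, the large-sample coverage of a nominal 95% CI for the rate ratio is 2Φ(1.96/√ratio) - 1.

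**(a) One sensation, three visits (m = 3): ratio (1-p)(1+2rho).**
- p = 0.3, rho = 0.8: 0.7 × 2.6 = 1.82, giving 85.4%.
- p = 0.5, rho = 0.5: 0.5 × 2.0 = 1.00, giving 95.0%.
- p = 0.5, rho = 0: 0.5 × 1 = 0.50, giving 99.4%.
- p = 0.7: even rho = 1 gives only 0.3 × 3 = 0.90, so the Poisson interval is too wide at every rho.

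Simulated coverage of the Poisson Wald CI (beta-binomial data, no true difference, 20 vs 20, 20,000 runs):

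| p | rho 0 | rho 0.3 | rho 0.5 | rho 0.8 |
|---|---|---|---|---|
| 0.1 | 98.0% | 94.1% | 91.0% | 88.1% |
| 0.3 | 98.3% | 94.1% | 90.6% | 85.8% |
| 0.5 | 99.5% | 97.2% | 94.8% | 91.3% |
| 0.7 | 100% | 99.6% | 98.8% | 97.1% |

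At p of 0.3 and above the simulation agrees closely with the formula. At p = 0.1 it is kinder than the formula (88.1% against 80.0% at rho 0.8); counts are small there, and only 87.4% of runs gave an estimable ratio in that cell. Results for 40 vs 20 are within about 2 points.

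**(b) Seven named sensations pooled over three visits (m = 21): ratio (1-p)(1+20rho).** At rho = 0.3 the second factor is 1 + 6 = 7.

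| p | Ratio | Coverage by formula | Simulated |
|---|---|---|---|
| 0.1 | 6.3 | 56.5% | 56.5% |
| 0.3 | 4.9 | 62.4% | 61.8% |
| 0.5 | 3.5 | 70.5% | 70.9% |
| 0.7 | 2.1 | 82.4% | 82.4% |

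At rho = 0.5 simulated coverage is 46-72%. At rho = 0 it is 96-100%, so the narrowness comes from the correlation. Little is needed: the ratio passes 1 once rho exceeds p/(20(1-p)), which is 0.021 at p = 0.3 and 0.117 at p = 0.7.

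**(c) Each participant counted once per sensation (m = 1).** The ratio is 1-p, always below 1. Simulated coverage is 99-100%, so the intervals are too wide.

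**Robust alternative.** Participant-level robust variance gives about 95-98% for three reports per person. For 21 pooled reports it gives about 95-97% at p 0.3-0.7 and 91-95% at p = 0.1.

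**The case against.** The strongest reply is that section 6.3 is silent on the variance estimator and does not exclude a robust one. That stands: the finding is conditional on the default model-based variance, which is the natural reading when nothing else is named. Silence elsewhere might be put down to house style, but the repeated-measures efficacy models state their subject random intercept explicitly.

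A reader might infer that the safety intervals are simply wrong, or always too narrow. The document does not support that. In case (a) coverage is 94.1% at p = 0.1 or 0.3 with rho 0.3, and nominal at p = rho = 0.5. In case (c) the intervals are conservative.

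A reader might also infer false-positive rates of 15-42%. Those arise for a total sensation count per person with mean 3-5 and between-person CV² of 0.3-1.0, where the variance ratio is 1 + mean × CV², from 1 + 3 × 0.3 = 1.9 to 1 + 5 × 1.0 = 6.0. The arithmetic is right, but section 6.3 announces no such total and the SAP gives neither value. Its reference to overall results is paired with results by group and reads as all participants, not all sensations.

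Finally, section 6.3 sets no safety hypothesis or significance threshold, and its promise to discuss minor differences can be read as a commitment to full reporting. That limits the consequence, but rate ratios with 95% CIs are still planned and will be read as having 95% coverage.

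**Conclusion.** The point holds in conditional form. Section 6.3 fixes a Poisson model for reports repeated within participants, accounts only for observation time, and defines neither the event nor the counting unit. Under model-based variance the intervals miss nominal coverage under most counting units. The error can be in either direction for one sensation over three visits, is clearly towards too narrow for pooled sensations with positive correlation, and is towards too wide for once-per-participant counting. They are about right only at particular combinations of p and rho.

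The sizes rest on assumed p and rho, on 20 per arm and, for pooling, on a common p and rho across the seven sensations. The effect is confined to the safety analysis; the primary efficacy result is untouched. It should be settled before the safety analysis is run.

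**What to change.** In section 6.3:

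1. State what intensity rating counts as an event, and whether the unit is the participant, the participant-visit, or the sensation-visit.
2. For repeated or pooled reports, estimate rates and rate ratios with participant-level robust (sandwich) variance, for example Poisson GEE clustered on participant.
3. For participant-level incidence of each sensation, report the proportion of participants with at least one report, with exact or Wilson CIs.

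This costs a few sentences in the SAP and one option in the software. CIs for pooled counts will be wider. With about 20 per arm the robust variance may fall a little short of nominal for uncommon sensations (91-95% for pooled reports at p = 0.1), against about 56% for the Poisson interval at p = 0.1 and rho = 0.3.

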6.4. Example table of baseline characteristics

Table 2. Baseline characteristics of the study sample.

	All (n =)	Cognitive training (n =)	PMR (n =)	Cognitive training + active tDCS (n =)	Cognitive training + sham tDCS (n =)
Demographics					
Age (years)					
Sex (F: M)					
Education (years)					
Cognitive data					
Auditory verbal learning					
Learning					
Immediate recall					
Delayed recall					
Recognition					
ROCF					

Statistical Analysis Plan

"Neuromodulation through brain stimulation-assisted cognitive training in patients with post-COVID-19 cognitive impairment (Neuromod- COV): study protocol for a PROBE phase IIb trial" Acronym: Neuromod-COV

Figure copy
Figure retrieval
Digit-span
Forward
Backward
TMT
Part A (sec)
Part B (sec)
Stroop test interference (sec)
Phonological fluency
Semantic fluency

Data are shown as mean (SD) or n (%). PMR: Progressive Muscle Relaxation; ROCF: Rey–Osterrieth Complex Figure *Test;* TMT: Trail Making Test

7. References

